12	STUDY CONDUCT RESPONSIBILITIES	. 28		
12.1	PROTOCOL AMENDMENTS, deviations and breaches	. 28		
12.2	2 STUDY RECORD RETENTION	. 28		
12.3	B END OF STUDY	. 28		
13	REPORTING, PUBLICATIONS AND NOTIFICATION OF RESULTS	29		
13.1	I AUTHORSHIP POLICY	29		
13.2	2 PUBLICATION	29		
13.3	B PEER REVIEW	29		
14	REFERENCES	. 29		

V3 31-08-2020 **PROTOCOL APPROVAL**

Understanding barriers to increasing physical activity in chronic pain: an exploratory study to develop the SUstainable Self Effective Exercise Development (SUSSED) intervention.

Signatures

The undersigned confirm that the following protocol has been agreed and approved by the Sponsor and that the Chief Investigator agrees to conduct the trial/study/study in compliance with this approved protocol and will adhere to the principles of GCP, the Sponsor SOPs, and any other applicable regulatory requirements as may be amended from time to time.

[name]

[name]

5th Dec 2019

Chief Investigator

Signature

Date

V3 31-08-2020

LIST OF ABBREVIATIONS

AE	Adverse Event	
АНР	Allied Health Professional	
CI	Chief Investigator	
CNORIS	Clinical Negligence and Other Risks Indemnity Scheme	
CRF	Case Report Form	
DMC	Data Monitoring Committee	
GCP	Good Clinical Practice	
GP	General Practitioner	
ICF	Informed Consent Form	
IF	Incidental Findings	
ISF	Investigator Site File	
РА	Physical Activity	
РІ	Principal Investigator	
PPI	Patient public involvement	
REC	Research Ethics Committee	
SAE	Serious Adverse Event	
SOP	Standard Operating Procedures	
S/TMF/SMF	Trial Master File/Study Master File	
T/SMG	Trial Management Group	
TPS	Tayside Pain Service	
TSC	Trial Steering Committee	

V3 31-08-2020

SUMMARY/SYNOPSIS

Study Title	Understanding barriers to increasing physical activity in chronic pain: an exploratory study to develop the SUstainable Self Effective Exercise Development (SUSSED) intervention.		
Study Design	Mixed methods observational study		
Study Population	Population 1: People with chronic (more than 6 months) pain referred to the NHS Tayside Pain Service.		
	Population 2: Key Stakeholders including healthcare professionals (e.g. General practitioners (GPs)/ Allied Health Professionals (AHP)s, Nurses, pharmacists); community organisations through the Green Health Partnership, Leisure Centre Staff		
Sample Size	Population 1 (people with chronic pa	ain): up to 45	
	Population 2 (stakeholders who might use SUSSED in patient care): Up to 16		
Planned study Period	1 year		
Clinical phase duration	Approximately 1 week		
Follow up phase duration	None		
Research Question 1	Objectives	Outcome Measures	
	Using a systematic approach, to understand barriers and facilitators to PA in patients with moderate-severe chronic pain	Qualitative analyses of semi- structured interviews with patients with moderate-severe chronic pain.	
Research Question 2	Using subjective and objective measures, to assess PA capacity and behaviour, and the	Qualitative analyses of semi- structured interviews with patients with moderate-severe chronic pain.	
	acceptability of these measures for future studies		
		Quantitative analysis of data obtained from validated Patient reported outcome measures of activity, personal fitness trackers and activPAL monitors	
Research Question 3	Using a systematic approach, to understand perceived barriers and facilitators in healthcare professionals and other stakeholders	Qualitative analyses of semi- structured interviews with healthcare professionals and other stakeholders to include the Green Health Partnership, and Leisure Centre Staff	

V3 31-08-2020

Research Question 4	To draw together the above outcome measures, our previous work, and best available published evidence to develop the SUSSED framework for future testing.	Development of the pilot SUSSED framework.	
Inclusion Criteria	Referred to Tayside pain service		
(Population 1)	In pain for at least 6 months		
	Pain severity: moderate to severe as assessed by pain clinic questionnaires (NRS>3)		
	No clinical contraindications to wearing Fitbit		
	Consented to being contacted for research		
	Over 18		
Exclusion Criteria	Receiving active treatment for cancer		
(Population 1)	Unable to provide informed consent		
Inclusion Criteria	Over 18		
(Population 2)	Member of stakeholder population, including healthcare professionals (e.g. General practitioners (GPs)/ Allied Health Professionals (AHP)s, Nurses, pharmacists); carers, 3rd sector organisations, leisure centre staff and others identified through the Green Health Partnership		
Exclusion Criteria	Unable to provide informed consent	Unable to provide informed consent	
(Population 2)			

V3 31-08-2020

1 INTRODUCTION

Chronic pain, affecting around 20% of adults (~45% of older adults), is the leading cause of disability globally and in Scotland (1). In the UK, with an aging demographic, societal burden of chronic pain is increasing, with a need to optimise management of this chronic condition. In parallel, there has been a marked increase in opioid prescribing, despite limited evidence base for long-term efficacy, and increasing concerns about harms: effective non-pharmacological strategies are urgently needed(2, 3).

There is good evidence, with recommendations from national and international guidelines, that physical activity (PA: bodily movement resulting in energy expenditure, in any context of daily life) is one of the few safe and effective interventions for chronic pain (4, 5). Our Cochrane review found that whilst PA is beneficial for chronic pain, there is insufficient evidence to recommend any particular PA type. Current evidence is low quality, often not including participants with moderate-severe pain or adequately measuring PA adherence (6-8). Exercise levels in those with chronic pain are poor: most (>90%) are very inactive. Patient beliefs are a strong factor in determining activity levels, with a need for clear, individualised advice and support (9). To date, there has been no systematic approach to identify how to best support individuals to increase PA, by addressing all relevant factors within a personalised plan, and using proven behaviour change techniques (6-8) (5).

It seems, therefore, that most people with chronic pain are not participating in one of the few known effective strategies to improve their health and functioning: PA should be an integral part of standard care.

We need to know how to best support these individuals to adopt and sustain regular PA. Understanding factors affecting engagement in regular PA is important. Barriers and facilitators are multifactorial, with physical, psychological, social and environmental factors playing varying roles. Barriers to PA may include pain itself, or fear of increased pain. Factors relating to the individual and the type of PA may influence engagement and adherence.

Gender, ethnicity, personal control, and peer and professional support may also impact on activity engagement and adherence (10). Additional, new barriers and influencing factors arising from factors associated with the COVID-19 pandemic may now also be important and lasting.

V3 31-08-2020

2 BACKGROUND & RATIONALE

Theory- and evidence-based approaches are recommended to inform development of complex interventions (11, 12). Many studies only address individual motivators and capabilities, without considering wider social and environmental factors(13). Overcoming barriers should include personalised approaches to changing behaviour, while understanding individuals' needs and concerns (6, 7). The Behaviour Change Wheel (BCW, see Figure 1 (14)), mapping to Behaviour Change Technique Taxonomy (BCT) (15) provides a validated theory-based approach to designing health behaviour change interventions ready for implementation.

[figure not shown]

Figure 1: The Behaviour Change Wheel (BCW) (14)

At the centre of the BCW is a system of factors directly influencing behaviour (the COM-B system: Capability (physical, psychological), Opportunity (social, physical) and Motivation (automatic, reflective)), encircled by interventional (education, persuasion, training, etc.); and policy (guidelines, legislation, social planning, etc.) factors that can promote or hinder (Figure 1). The relative importance of each factor will differ between individuals. This approach has not been applied in any previous chronic pain trials, or activity-based interventions. This study is not intended to evaluate any specific behaviour change technique, but to develop a Framework for applying the right technique to the right person. If possible, the SUSSED Framework will map to proven behaviour change techniques, but this will not be possible for all techniques (e.g. improving access to public transport).

V3 31-08-2020

3 TRIAL/STUDY OBJECTIVES & OUTCOMES

Table 1: Research questions and Outcome Measures

Research Question	Outcome Measure:	Timepoint of outcome measured	
Research question 1: Using a systematic approach, to understand barriers and facilitators to PA in patients with moderate-severe chronic pain	Qualitative analyses of semi- structured interviews with patients with moderate-severe chronic pain.	Study appointment 1	
Research Question 2: Using subjective and objective measures, to assess PA capacity and behaviour, and the	 Qualitative analyses of semi- structured interviews with patients with moderate-severe chronic pain. 	Study appointment 1	
acceptability of these measures for future studies	 Quantitative analyses of questionnaires 	 Study appointment 1 and Study appointment 2 (about one week 	
	• Quantitative analysis of data obtained from personal fitness trackers may include; step count, distance covered, flights of steps climbed, length of sleep, calories burned.	 apart) Between Study appointment 1 and 2 (about one week) 	
	 Analysis of questionnaire of acceptability of wearing activity trackers 	• Study appointment 2	
Research question 3: Using a systematic approach, to understand perceived barriers and facilitators in healthcare professionals and other stakeholders	 Qualitative analyses of semi- structured interviews with healthcare professionals and other stakeholders. 	Single interview per stakeholder at one timepoint during study	
Research question 4: To draw together the above outcome measures, our previous work, and best available published evidence to develop the SUSSED framework for future testing.	 Development of the SUSSED framework. 	Development to occur following data collection, analysis and synthesis of evidence	

V3 31-08-2020

4 TRIAL/STUDY DESIGN

4.1 INTERVENTION

This is a non-interventional study.

4.2 TRIAL/STUDY DESCRIPTION

This study will enable the development of the SUSSED framework, using a mixed methods approach.

Up to 45 people referred to the Tayside pain service will be invited to take part in the study, aiming for a total of 40 completing the first study appointment.

They will take part in a semi-structured interview designed to assess their perceptions of the barriers and facilitators to their participation in PA.

In addition, participants will be asked to complete a questionnaire, which includes 7 validated self-report questionnaires to collect information about their pain severity, and its impact, as well as attitudes to physical activity. Demographic and basic clinical information including age, gender, height and weight will be collected together with underlying diagnosis, other co-morbidities, and postcode to enable Scottish index of multiple deprivation to be recorded.

Participants will then be provided with an activPAL4[™] activity monitor (http://www.palt.com/pals/) and asked to wear this for 1 week. 20 participants who consent to wearing a Fitbit monitor will be asked to wear a Fitbit Charge 3 (https://www.fitbit.com/uk/charge3) monitor in addition to the activPAL monitor. Both the activPAL and FitBit trackers are CE marked.

Participants will be contacted after 1 week and will then be asked to complete the questionnaire as before. We will also use a number of brief questions around acceptability and feasibility of monitor use, based on our previous work (to include questions such as "did you have any problems while wearing the monitor ?"; "did you remove the monitor for any reason?"; "were there any times when you forgot to wear the monitor?" and "were there any times when you decided not to wear the monitor?"; "did you have any pain or discomfort wearing the monitor?"). Their fitness trackers will be collected and data downloaded.

To assess how behaviour change components and techniques identified by analysis of the data collected from patients can be applied in practice through existing processes and infrastructure, representative stakeholders including specialist and community-based healthcare practitioners (GPs, pharmacists, physiotherapists), carers, 3rd sector organisations, leisure centre staff and others identified through the Green Health Partnership will be interviewed. The semi-structured interviews will focus on the BCW (Figure 1), and potential mapping to the BCT including the logistics, feasibility and stakeholders' opinions of any potential interventions.

Patient and stakeholders' interviews will be recorded, transcribed and inductively analysed into themes mapped to the 22 BCW categories (Figure 1), and any other themes that arise, assessing their nature and relative importance. Objective data from questionnaires and function measurements will be processed using standard protocols and reported using descriptive statistics. ActivPAL data will be analysed using an event-based approach

V3 31-08-2020

(assessing continuous periods of a single activity, e.g. walking) to allow an assessment of the quantity, pattern and timing of actual physical activity (20). Derived outcome measures will include, time spent sitting, standing and walking and time spent walking at a moderate intensity. Data from FitBitTM monitors will be collected through agreed shared access to each participant's personal FitBitTM web page. Important data will be number of steps, but will also include recorded daily distance walked, flights of stairs climbed and periods of prolonged activity. This data will be used to inform application of the SUSSED Framework, particularly in relation to assessing PA and physical capability. Collecting data from several sources allows comparison and assessment of relative (concurrent) validity, to inform future trial design and outcome measurement. Although objective monitors report walking related outcomes, other outcomes include duration and pattern of sitting (activPAL), heart rate (Fitbit), and some activity types e.g. swimming (Fitbit). This study is not primarily about assessing PA levels, but about developing the intervention and identifying how to best evaluate it in future.

Comparative analysis will explore associations between qualitative data that might affect the behaviour change response to the SUSSED Framework.

In recognition of the impact of the COVID19 pandemic on, and the uncertainties surrounding healthcare delivery, we will offer the option of video or telephone assessments, to minimise risk to participants and researchers. If face to face interviews are carried out, then appropriate, recommended safety precautions will be used.

V3 31-08-2020

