4.10 NUMBER OF PARTICIPANTS

Population 1

A maximum of 45 patients, to achieve a total to 40 patients completing the first study appointment, will be recruited over a period of 4 months.

Population 2

Up to 16 stakeholders will take part in a one-off interview.

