4.11 INCLUSION CRITERIA

Population 1

- Referred to Tayside pain service
- Pain present for at least 6 months
- No clinical contraindications to wearing Fitbit
- Consented to being contacted for research
- Pain severity: moderate to severe as assessed by pain clinic questionnaires (NRS>3)
- Over 18

Population 2

- Over 18
- Member of stakeholder population, including healthcare professionals (e.g. General practitioners (GPs)/ Allied Health Professionals (AHP)s, Nurses, pharmacists); carers, 3rd sector organisations, leisure centre staff and others identified through the study team, with the Green Health Partnership and Pain Concern/ Versus Arthritis.

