6.1.2.2 Fitness tracker data

Participants will be instructed on how to fit the activPAL monitor at study appointment 1 and advised to wear this continuously for seven days. At the second, remote study appointment they will be instructed how to remove the trackers and how to return them to the study team They will be given an instruction leaflet on how to fit, use and remove the activPAL trackers. Trackers will either be collected and returned to the study team by courier or collected by a member of the study team, while observing social distancing guidelines. The data from the activPAL trackers will be downloaded onto University of Dundee servers where it will be identified using a study ID number. ActivPAL data will be analysed using an event-based

V3 31-08-2020

approach (assessing continuous periods of a single activity, e.g. walking) to allow an assessment of the quantity, pattern and timing of actual physical activity (20). Derived outcome measures will include, time spent sitting, standing and walking and time spent walking at a moderate intensity.

20 participants will also be asked to wear a Fitbit. The study team will create individual Fitbit accounts for each of these participants. These accounts will not use the individuals' real names, and will be linked to email accounts generated by the University of Dundee IT. Participants' date of birth, gender, height and weight will be entered into the accounts. Location service will be disabled on the Fitbit account. Fitbit have agreed to a take over by Google, and terms of this agreement are likely to be settled in 2020. At the moment we cannot be sure what the implications of this agreement will be. Both companies have issued statements that they will respect existing policies on data storage and sharing. Since some people may not be in agreement with sharing their data with multinational companies such as Fitbit or Google, we will provide the option to consent to wearing the ActivPAL only. Data from FitBit monitors will be downloaded from the individual accounts opened for each participant. Important data will be the number of steps, but will also include recorded daily distance walked, flights of stairs climbed and periods of prolonged activity. These data will be extracted from the Fitbit accounts of individual accounts into Excel spreadsheets. Data will be saved in an anonymised format using study ID.

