7 STATISTICS AND DATA ANALYSIS

7.1 SAMPLE SIZE CALCULATION

No formal sample size calculation was made for this exploratory study. We are aiming for a total of 40 patients completing the first study appointment. While we do not anticipate a high dropout rate from participants who have actively expressed an interest in taking part, there may be unforeseen circumstances that prevent study appointments being conducted, even after an appointment has been agreed. The non-attendance rate at routine clinic appointments is 12-15%, so we have extrapolated this to allow for up to an additional 5 patients being approached/ appointed (ie a total of 45, or 40 patients, whichever is reached sooner).

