7.2.2 Quantitative analysis

7.2.2.1 Fitness tracker

An assessment of the level of PA undertaken by each participant will be made by analysing the variables, which include:

Feasibility outcomes: Number of days worn; Reported problems with wearing the monitor; Reported pain or discomfort while wearing the monitor; Reported duration and reasons for removing the monitor early (activPAL) or not wearing the monitor (FitBit).

Primary physical activity outcomes that are comparable between monitors:

Number of steps taken; Time spent in MVPA (moderate to vigorous physical activity). [For the activPAL this will be assessed as the time spent walking at a cadence of >= 100 steps/minutes; for the FitBit this will be the sum of time spent "fairly active" and time spent "very active"]

Secondary exploratory physical activity outcomes:

For the activPAL:

Total time spent walking; Time sent standing; Number of sit to stand transitions; Time spent sitting; Time spent in prolonged (>=30minutes) sitting (waking hours)

For the FitBit: Distance walked; Number of floors climbed; Time spent sedentary; Time spent in light activity; Time in bed; Time asleep; Time awake; Number of awakenings; Time spent in n REM, light and deep sleep

Three types of analysis will be conducted:

(1) Feasibility of using the monitors will be established by descriptive information on the quantity (number of days worn) and quality (usable days of data) of data collected from each monitor. Descriptive information will be gathered on comfort of use and reasons for non-wear, from the feasibility questionnaire.

V3 31-08-2020

(2) The cross-sectional daily physical activity (including patterns of activity) of participants will be reported using descriptive statistics. This information will be used to characterise participants, and individual physical activity levels will be used in conjunction with interview information to develop the SUSSED framework.

(3) For people who wore both the activPAL and the Fitbit, the concurrent agreement of the primary physical outcomes outcome measures (which are assessed by both monitors) will be assessed.

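### The Fitbit contraindication criterion bars people from the whole patient study although only 20 wear a Fitbit, and Fitbit feasibility leaves out those who decline or cannot wear one

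*Protocol*

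**What the plan says.** All patients in Population 1 are to wear an activPAL for a week. For the second device, section 4.2 says "20 participants who consent to wearing a Fitbit monitor will be asked to wear a Fitbit Charge 3". Section 6.1.2.2 foresees that some will object to their data reaching large technology companies and adds: "we will provide the option to consent to wearing the ActivPAL only".

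The Population 1 inclusion criteria (synopsis and section 4.11) nevertheless contain "No clinical contraindications to wearing Fitbit", with no restriction to the Fitbit subset and no reason given.

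Section 7.2.2.1 begins its list of tracker outcomes with "Feasibility outcomes: Number of days worn; Reported problems with wearing the monitor" and continues with discomfort, early removal of the activPAL and non-wear of the Fitbit. The sample acceptability questions in section 4.2 ask about experience while wearing a monitor. Uptake and refusal of the Fitbit are not listed.

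On numbers, section 4.10 gives "A maximum of 45 patients, to achieve a total to 40 patients completing the first study appointment", and section 7.1 states "No formal sample size calculation was made for this exploratory study".

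**The concern.** There are two separate problems.

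**Eligibility.** A requirement that matters only for Fitbit wearers decides entry to everything else. A patient who refuses the Fitbit over data sharing can stay in with the activPAL alone; a patient who cannot wear it for a clinical reason cannot enter at all. This sits badly with section 5, which gives the aim as finding the exercise barriers of the chronic pain population as a whole and takes care not to lose people who lack videocall equipment. Research question 1 rests on the interviews, where no Fitbit is involved.

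**Feasibility.** Research question 2 asks whether the measures are acceptable for future studies, and section 4.5.3 says the Fitbit experience will inform outcome measurement in them. For that purpose, willingness and ability to wear the device count as well as comfort among those who wear it. The protocol expects refusals but does not list them as an outcome, and it screens out those unable to wear the device before they could be counted.

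**Working it through.** **The plan's own figures.** Section 7.1 reaches 45 from 40 with the statement "The non-attendance rate at routine clinic appointments is 12-15" per cent.
- At 12%: 40 × 1.12 = 44.8, rounded up to 45; 40 / 0.88 = 45.5, rounded up to 46.
- At 15%: 40 × 1.15 = 46; 40 / 0.85 = 47.1, rounded up to 48.

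So 45 is reproduced at the lower end of the range. It matters here only as a cap on enrolment. The Fitbit number of 20 has no derivation.

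**Share to whom the criterion is irrelevant.** With N patients and 20 wearers, the non-wearers are (N − 20)/N:
- N = 40: 20/40 = 50%.
- N = 45: 25/45 = 55.6%.

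**How many the criterion might exclude.** The protocol neither defines the contraindications nor gives their frequency. If a proportion c of otherwise eligible patients has one (assumption), the expected number excluded per 40 enrolled is 40c/(1 − c):
- c = 1%: 0.4
- c = 2%: 0.8
- c = 5%: 2.1
- c = 10%: 4.4

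**What the missing denominator could do.** Let d be the number offered the Fitbit who decline. Uptake is 20/(20 + d). If x of the 20 wearers find it acceptable, acceptability among those offered is x/(20 + d). The protocol gives neither d nor x. The table assumes x = 18, with exact 95% intervals.

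| Decliners d | Offered | Uptake | Acceptable among offered (95% CI) |
|---|---|---|---|
| 0 | 20 | 100% | 90% (68.3 to 98.8) |
| 2 | 22 | 91% | 82% (59.7 to 94.8) |
| 5 | 25 | 80% | 72% (50.6 to 87.9) |
| 10 | 30 | 67% | 60% (40.6 to 77.3) |
| 20 | 40 | 50% | 45% (29.3 to 61.5) |

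People unable to wear the device would enlarge the denominator in the same way. The possible gap therefore runs from nothing to a halving, and only a record of offers can say where the study lies.

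**Whether this can be settled later.** Section 7.2 has the analysis plan finalised before data lock. An analysis plan cannot change who was eligible, nor supply counts that nobody kept. Section 6.2 limits the case report form to what the study aims require, and section 5.4 has ineligible people take no further part, so patients screened out for a contraindication may leave no record.

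**The case against.** The strongest reply is that wear and comfort can be observed only in people who agree to wear the device, so conditioning on consent is unavoidable. The one refusal reason the protocol names is data sharing, which need not distort reports of comfort. That stands: the gap is the missing count of offers and refusals, not the consent step, and nothing here weakens the planned activPAL–Fitbit comparison.

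A reader might go further and infer that Fitbit acceptability *is* overstated, or that the 20 to 25 non-wearers are refusals. The documents support neither. The number 20 is a quota, so non-wearers may never have been offered the device, and with no decliners and nobody unable there is no overstatement. Nor does the plan promise a single feasibility proportion; it plans descriptive reporting.

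A reader might also assume that the places go to whoever consents first, or that the criterion removes people with wrist or skin problems. The protocol does not say how the 20 are chosen if more agree, and it does not define the contraindications. That the activPAL has no matching criterion, although section 4.6 mentions a skin reaction, is not in itself an error; the same section sets out precautions.

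Finally, the outcome list in section 7.2.2.1 is not exhaustive, and section 5.2 has consent conversations logged, so some counts may be recoverable. This softens the second problem without removing it: nothing requires reasons for declining to be recorded, or makes uptake an outcome. It does not touch the first.

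**Conclusion.** Both parts hold in limited form. The Fitbit criterion reaches the whole of Population 1 although it is relevant to 20 of 40 to 45 patients, activPAL-only participation is allowed, and the stated aim is broad. That rests on the text alone. The number of people lost is unknown and may be small: between 0.4 and 4.4 per 40 enrolled if 1% to 10% have a contraindication, which is an assumption.

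The Fitbit feasibility outcomes describe only those who agree to wear one, so the device's suitability for a future trial may be overstated. The size cannot be computed from the protocol; it is nil if nobody declines or is unable. The table above is an illustration, not an estimate. The change is worth making because it is cheap and because offers and refusals not recorded at the time cannot be recovered afterwards.

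**What to change.** 1. In the synopsis and section 4.11, apply the Fitbit criterion to the Fitbit subset only, so that patients with a contraindication can join as activPAL-only participants.
2. In section 4.2 or 6.1.2.2, state how the 20 are chosen: offer the Fitbit to consecutive participants until 20 have accepted.
3. In section 7.2.2.1, add as a feasibility outcome the numbers offered the Fitbit, unable to wear it, declining (with reason) and accepting, recorded prospectively. The denominator should contain only those actually offered the device or found unable to wear it, not participants enrolled after the 20 places are filled.

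Offering the Fitbit to every second participant would be a poor alternative. Under the cap of 45 it gives 22 or 23 offers, so 20 wearers would need 20/23 = 87% to 20/22 = 91% acceptance. At an assumed 50% acceptance only about 11 would wear one, which would weaken the agreement analysis.

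The cost is a minor amendment, a short offer log, and slightly fewer enrolled patients able to fill the 20 places. If 10% of 40 were contraindicated (assumption), 36 would remain, and the acceptance needed would rise from 20/40 = 50% to 20/36 = 56%.
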